Surgical specimens obtained during the routine surgery and any ONM-100 fluorescence guided biopsies will be prepared using standard specimen processing methods and timelines. Specimens will be sampled and analyzed according to routine pathologic evaluation.

After surgery, the patient will be strictly observed following the standard, respective, postoperative protocol. Patients will be monitored for safety assessments and sample procurement.

Medical history, prior medication use, hemoglobin, and Karnofsky performance status will be evaluated at Screening and pretreatment on Day 0. Pregnancy tests will be performed at Screening and at Day 28 (\pm 5 days). Electrocardiograms (ECGs) will be performed pretreatment, at 30 \pm 10 minutes postdose on Day 0 and Day 10 (\pm 5 days).

Patient safety will be assessed for 28 days (\pm 5 days). All patients will be monitored for vital signs and physical examination pretreatment and at various time points up to Day 10 (\pm 5 days). All patients will be monitored for comprehensive metabolic panel (CMP) and complete blood count (CBC) with differentials pretreatment and at various time points up to Day 28 (\pm 5 days). All patients will be monitored for treatment-emergent adverse events (TEAEs) and concomitant medication use from the start of dosing up to Day 28 (\pm 5 days). TEAEs will be followed closely during the study to identify any potential DLTs.

Number of Patients

Up to 60 patients will be enrolled in this study (with planned allocation of up to 15 patients in up to 5 cohorts in Part 1, approximately 10 to 20 patients in Part 2, and approximately 20 to 30 patients in Part 3). The actual number of patients in Part 1 and Part 2 may vary, depending on the number of Part 1 cohorts and Part 2 Groups/tumor types that are activated for enrollment.

All patients will receive a single dose of ONM-100 followed by routine surgery and pathology of the respective solid cancer. Based on the ON-1001 study experience, we estimate that 3 patients for each dose is sufficient for safety and imaging feasibility evaluations in Part 1. Each patient's tumors will be imaged intraoperatively and at planned sites post operatively. For those patients with fluorescence in the surgical wound bed after standard procedures, tissue biopsy may be taken at surgeon's or pathologist's discretion. Up to 3 additional patients may be enrolled in the event of a DLT.

Inclusion Criteria

Patients must meet the following inclusion criteria:

- 1. Adults ≥ 18 years of age
- 2. Biopsy-confirmed diagnosis, for primary or recurrent disease (or high clinical suspicion in the opinion of the Investigator)
 - a. Part 1: Stage 0 to 4
 - b. Part 2:
 - Stage 0 to 4
 - Stage 2 to 4
 - c. Part 3:
 - Stage 2 to 4 Including
- 3. Acceptable hematologic status (as standard surgery protocol requires, as determined by the Investigator), kidney function and liver function. Elevations of creatinine, alanine aminotransferase, aspartate aminotransferase, alkaline phosphatase, or total bilirubin >1.5× the upper limit of normal [ULN] must be determined to be not clinically significant by the Investigator and approved by the Medical Monitor.
- 4. Documented negative serum pregnancy test for women of childbearing potential (ie, premenopausal women with intact reproductive organs and women <2 years after menopause)
- 5. Male patients and female patients of child-bearing potential (ie, premenopausal women with intact reproductive organs and women <2 years after menopause) must agree to and comply with using medically acceptable contraception including surgical sterilization (eg, hysterectomy, bilateral oophorectomy, bilateral tubal ligation), intrauterine device, oral contraceptive, contraceptive patch,

long acting injectable contraceptive, partner's vasectomy, double-barrier method (condom or diaphragm plus spermicide or condom plus diaphragm), or abstinence during the trial and for 6 months thereafter 6. 7. Adequate potential for follow up 8. Willing and able to provide written informed consent **Exclusion Criteria** Patients must NOT meet any of the following exclusion criteria: 1. Histologically diagnosed by an excisional biopsy procedure 2. **** 3. Life expectancy <12 weeks 4. Karnofsky Performance Status <70% 5. Hepatic impairment (Child-Pugh score >5) or significant liver disease including active hepatitis or cirrhosis 6. Lab values or any sign, symptom, or medical condition that in the opinion of the PI would prevent surgical resection 7. Medical or psychiatric conditions that compromise the patient's ability to give informed consent. 8. Pregnant or lactating women 9. 10. 11. 12. Receiving or planned to receive, during the duration of the study, concomitant medication with a high chance of h 14. Received an investigational agent within the shorter of 5 half-lives or 30 days before ONM-100 dosing 15. Inability to adhere to the schedule of assessments or any circumstance that would interfere with the validity of assessments performed in the study 16. The PI considers that the patient should not participate in the study Test Product, Dose and Mode of Administration

Comparator

There is no comparator imaging agent used in this study.

Expected Duration of Patient Participation

In Part 1, study participation will require 28 days (±48 hours), not counting the prestudy screening visit from Day -30 to Day -1. Following a single dose of ONM-100 administered by IV infusion on Day 0,

are considered clinically significant by the Investigator, will be repeated on Day 28 (±48 days). All TEAEs and abnormal laboratory findings that are considered at least possibly related to ONM-100 will be followed until resolved or stabilized.

In Part 2, study participation will require 28 days (\pm 5 days), not counting the prestudy screening visit from Day -30 to Day -1. Imaging is performed during surgery. Surgery could be on the same day as ONM-100 dosing

abnormal laboratory findings that are considered at least possibly related to ONM-100 will be followed until resolved or stabilized.

In Part 3, study participation will require 28 days (±5 days), not counting the prestudy screening visit from Day -30 to Day -1.

All TEAEs and

All TEAEs and

abnormal laboratory findings that are considered at least possibly related to ONM-100 will be followed until resolved or stabilized.

Criteria for Evaluation

Efficacy Analyses

In Part 1 and Part 2, ONM-100 fluorescence from in vivo and excised tissues will be imaged using intraoperative and post-operative NIR cameras and will be correlated with the histopathological confirmation of tumor and normal tissues to determine ONM-100's diagnostic performance.

In Part 3, the intraoperative fluorescence status of collected primary tumor, SOC and ONM-100 guided biopsies, as well as lymph nodes will be compared to histological analyses of the collected specimens.

Safety Analyses

Safety assessments will include the following safety related parameters:

- TEAE incidence, severity, and relationship to study drug
- Physical examination
- Vital signs
- ECGs
- Clinical laboratory (CMP, hemoglobin, and CBC with differentials)

Pharmacokinetic Analyses

Characterization of the ONM-100 PK profile will include the following major PK parameters:

- Maximum plasma concentration (C_{max})
- Time to C_{max} (T_{max})
- Area under the time-concentration curve (AUC)
- Total body clearance (CL)
- Volume of distribution (Vz)
- Volume of distribution at steady state (Vss)
- Elimination rate constant (λz)
- Terminal elimination half-life (t_{1/2})

Statistical Methods

This is a pilot study with the intention of gathering data to assess feasibility and imaging metrics for the efficacy analysis. Therefore, no formal statistical hypothesis testing will be performed for making development decisions.

Analysis populations

- Safety Population: all patients who receive any dose of ONM-100
- Efficacy Population: all patients who received any dose of ONM-100 and who have sufficient imaging and pathology analysis data to calculate fluorescence intensity and pathology correlation for ≥1 tumor sample
- Pharmacokinetic Population: all patients who receive ONM-100 and who have sufficient ONM-100
 plasma concentration data to calculate ≥1 PK parameter.

Sample Size Calculation

Given the exploratory nature of the study, formal sample size calculations were not performed.

Protocol Amendment 6.0

Safety Analyses

The safety analyses will be in the Safety Population.

Adverse events (AEs), vital signs, ECGs, and conventional clinical laboratory data (CMP and CBC with differentials) will be summarized using descriptive statistics.

Adverse events will be coded using the Medical Dictionary for Regulatory Activities (MedDRA) Version 21.1. The incidence of TEAEs will be presented by system organ class and preferred term, by relationship to study drug, by severity, and by whether or not they resulted in alteration of administration of or discontinuation of study drug. A TEAE is defined as an AE that occurs during or after study drug administration and up through 28 days (±48 hours) in Part 1 and up through 28 days (±5 days) in Part 2 and Part 3 after administration of study drug. In addition, the incidence of serious TEAEs and TEAEs leading to discontinuation of study drug will be presented by system organ class, preferred term, and relationship to study drug.

Descriptive statistics for clinical laboratory test results and vital signs, and for changes from Baseline, will be presented by time point. Baseline is defined as the measurement closest to, but before, the administration of study drug. Incidences of potentially clinically meaningful clinical laboratory results and vital signs, determined based on normal ranges and percentage changes from Baseline, will also be summarized by time point. The number and percentage of abnormal ECGs will be provided by time point.

Pharmacokinetic Analyses

The PK analyses will be assessed in the Pharmacokinetic Population.

Plasma concentration-time profiles will be constructed for each patient and each dosing cohort. Plasma concentration values will be summarized at each time point using mean, standard deviation, median, and range.

Summary PK parameters will be summarized using mean, standard deviation, median, and range.

Figure 1: Schematic of Study Design (Part 1 and Part 2)

Based on review of safety and fluorescence data from previously treated cohorts, actual doses selected may be smaller increases from the dose studied in the previous cohort, or may be an intermediate dose between previously studied doses

Protocol Amendment 6.0

Confidential

Page 15 of 125

Table 3: Schedule of Assessments and Procedures (Part 1 all cohorts)

| Study Day | -30 to -1 | | 1 (±4h) | 3 (±24h) | 6 (±24h) | 28 (±48h) | | |
|---|------------------------|-------------------|------------------------------|--|----------------|--------------|-------|---|
| | Screening ^a | Pre- treatment | Study Drug Administration | Surgery (3±2h or an alternate imaging schedule TBD) | | Follo | ow-up | |
| Informed consent ^b | X | | | | | | | |
| Medical history | X | Х | | | | | | |
| Vital signs | Х | Х | X ° | | X ^d | | Х | |
| Complete physical examination | Х | | | | | | Х | |
| Height, weight, BMI calculation | Х | Х | | | | | | |
| Calculate Child-Pugh score Encephalopathy Ascites INR or PT prolongation in seconds | X | | | | | | | |
| 12-lead ECGs | | Xe | Xe | | | | Х | |
| Blood for CMP ^{f,} | Х | Xg | | | Х | Х | Х | Х |
| Blood for CBC with differentials | Х | X ^g | | | Х | | Х | Х |
| Blood for HgbA1C | Х | X ^g | | | | | | |
| Pregnancy test ^h | Х | | | | | | | Х |
| Perform test for alcohol ⁱ | | Х | | | | | | |
| Karnofsky Performance Status Scale | Х | Х | | | | | | |
| Confirm study eligibility | Х | Х | | | | | | |
| Administration of ONM-100 ^j | | | Х | | | | | |

| Study Day | -30 to -1 | | | 1 (±4h) | 3 (±24h) | 6 (±24h) | 28 (±48h) | |
|-------------------------------------|------------------------|-------------------|------------------------------|--|-------------|-------------|--------------|---|
| | Screening ^a | Pre- treatment | Study Drug Administration | Surgery (3±2h or an alternate imaging schedule TBD) | | Follo | ow-up | |
| | | | | \times | | | | |
| | | | | X | | | | |
| | | | | Х | | | | |
| | | | | Х | | | | |
| | | | | | | | | |
| | | | | | | | | |
| Plasma for PK analyses ^m | | X | Х | | Х | Х | Х | |
| Assess for TEAEs ⁿ | | | Х | Х | Х | Х | Х | X |
| Prior/concomitant medications | Х | Х | Х | Х | Х | Х | Х | Х |

Protocol Amendment 6.0

Confidential

Page 17 of 125

Table 4: Schedule of Assessments and Procedures (Part 2 when ONM-100 dosing on day of surgery)

| Study Day | -30 to -1 | 0 | | | 1 (±8 hours) | 10 (±5 days) | 28 (±5 days) |
|--|------------------------|-------------------|------------------------------|------------------|--------------------|--------------------|--------------------|
| | Screening ^a | Pre- treatment | Study Drug Administration | Surgery (TBD) | F | ollow-up | • |
| Informed consent ^b | X | | | | | | |
| Medical history | х | Х | | | | | |
| Vital signs | X | Х | X ° | | Xď | Х | |
| Complete physical examination | X | | | | | Х | |
| Height, weight, BMI calculation | Х | Х | | | | | |
| Calculate Child-Pugh score Encephalopathy Ascites INR or PT prolongation in seconds | х | | | | | | |
| 12-lead ECGs | | Xe | Xe | | | Х | |
| Blood for CMP ^f | X | Xg | | | Х | Х | X |
| Blood for CBC with differentials | х | Xg | | | Х | Х | Х |
| Blood for HgbA1C | X | Х | | | | | |
| Pregnancy test ^h | X | | | | | | Х |
| Perform test for alcohol ⁱ | | Х | | | | | |
| Karnofsky Performance Status Scale | X | Х | | | | | |
| Confirm study eligibility | X | Х | | | | | |
| Administration of ONM-100 ^j | | | Х | | | | |
| | | | | х | | | |
| | | | | X | | | |

| | | | | х | | | |
|-------------------------------------|---|---|---|---|---|---|--------|
| | | | | х | | | |
| | | | | | | | |
| Plasma for PK analyses ^m | | Х | Х | | Х | | |
| Assess for TEAEs ⁿ | | | X | Х | Х | X | X |
| Prior/concomitant medications | Х | X | X | Х | Х | Х | Х |
| | | | | | | | \sim |

Footnotes for Table 4

Confidential

| Table 4A: Sch | edule of Assessments and | l Procedures (P | Part 2 when C | ONM-100 dosing | 16-80 hours before surg | gery) |
|---------------|--------------------------|-----------------|----------------------|----------------|-------------------------|-------|
|---------------|--------------------------|-----------------|----------------------|----------------|-------------------------|-------|

| Study Day | -30 to -1 | | 0 | 1 (or longer) ^b | | 28 (±5 days) |
|---|------------------------|-------------------|------------------------------|-------------------------------|-------|--------------------|
| | Screening ^a | Pre- treatment | Study Drug Administration | Surgery (16-80 h postdose) | Follo | w-up |
| Informed consent ^c | Х | | | | | |
| Medical history | X | X | | | | |
| Vital signs | х | X | X ^d | X ^{e,f} | х | |
| Complete physical examination | Х | | | | х | |
| Height, weight, BMI calculation | Х | Х | | | | |
| Calculate Child-Pugh score Encephalopathy Ascites INR or PT prolongation in seconds | х | | | | | |
| 12-lead ECGs ^g | | X | Х | | х | |
| Blood for CMP ^h | х | X ⁱ | | Xf | х | Х |
| Blood for CBC with differentials | Х | Xi | | Xf | х | Х |
| Blood for HgbA1C | Х | Xi | | | | |
| Pregnancy test ^j | Х | | | | | Х |
| Perform test for alcohol ^k | | X | | | | |
| Karnofsky Performance Status Scale | х | X | | | | |
| Confirm study eligibility | Х | Х | | | | |
| Administration of ONM-100 ¹ | | | Х | | | |
| | | | | Х | | |

| Study Day | -30 to -1 | 0 | | 0 | | 0 | | 0 | | 1 (or longer) ^b | 10 (±5 days) | 28 (±5 days) |
|-------------------------------|------------------------|-------------------|------------------------------|-------------------------------|--------|------|--|---|--|-------------------------------|--------------------|--------------------|
| | Screening ^a | Pre- treatment | Study Drug Administration | Surgery (16-80 h postdose) | Follow | w-up | | | | | | |
| | | | | X | | | | | | | | |
| | | | | Х | | | | | | | | |
| | | | | Х | | | | | | | | |
| | | | | | | | | | | | | |
| Plasma for PK analyses ° | | x | X | Xf | | | | | | | | |
| Assess for TEAEs ^p | | | X | X ^f | X | X | | | | | | |
| Prior/concomitant medications | Х | Х | Х | Xf | Х | X | | | | | | |

Protocol Amendment 6.0

Confidential

Confidential

Table 5:Schedule of Assessments and Procedures (Part 3)

| Study Day | -30 to -1 | 0 | | 1 ^b | 10 (±5 days) | 28 (±5 days) |
|---|------------------------|-------------------|------------------------------|--------------------------------------|--------------------|--------------------|
| | Screening ^a | Pre- treatment | Study Drug Administration | Surgery (24 ±8 hours postdose) | Follow | w-up |
| Informed consent ^c | х | | | | | |
| Medical history | х | X | | | | |
| Vital signs | Х | X | X ^d | X ^{e,f} | х | |
| Complete physical examination | Х | | | | х | |
| Height, weight, BMI calculation | Х | X | | | | |
| Calculate Child-Pugh score Encephalopathy Ascites INR or PT prolongation in seconds | х | | | | | |
| 12-lead ECGs ^g | | X | Х | | X | |
| Blood for CMP ^h | Х | X ⁱ | | X ^f | х | X |
| Blood for CBC with differentials | Х | Xi | | Xf | X | X |
| Blood for HgbA1C | Х | Xi | | | | |
| Pregnancy test ^j | Х | | | | | Х |
| Perform test for alcohol ^k | | Х | | | | |
| Karnofsky Performance Status Scale | Х | Х | | | | |
| Confirm study eligibility | Х | Х | | | | |
| Administration of ONM-100 ¹ | | | Х | | | |
| $\times\!\times\!\times\!\times\!\times\!\times\!\times\!\times\!\times\!\times\!\times\!\times\!\times\!\times\!\times$ | | | | Х | | |
| | | | | Х | | |

| Study Day | -30 to -1 | 0 | | 1 ^b | 10 (±5 days) | 28 (±5 days) |
|--|------------------------|-------------------|------------------------------|--------------------------------------|--------------------|--------------------|
| | Screening ^a | Pre- treatment | Study Drug Administration | Surgery (24 ±8 hours postdose) | Follow | v-up |
| | | | | Х | | |
| | | | | Х | | |
| $\times\!\!\times\!\!\times\!\!\times\!\!\times\!\!\times\!\!\times\!\!\times\!\!\times\!\!\times\!\!\times\!\!\times\!\!\times\!\!$ | | | | Х | | |
| $\times\!\!\times\!\!\times\!\!\times\!\!\times\!\!\times\!\!\times\!\!\times\!\!\times\!\!\times\!\!\times\!\!\times\!\!\times\!\!$ | | | | | | > |

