- Part 2 will be a verification of the dose(s) and imaging schedule(s) from Part 1. Approximately 10 to 20 patients will be enrolled in Part 2. Eligible patients will have a confirmed diagnosis (or high clinical suspicion in the opinion of the Investigator) from among the following list of solid tumor types
 Initial enrollment will begin with prostate and ovarian cancer patients only. Eligible tumor types will be opened and/or closed to enrollment based on continuous review of imaging results. The Sponsor will inform Investigators which tumor types are open to enrollment during the conduct of Part 2.
- In Part 3, the dose and tumor type selection is based on information available from the results of all previous doses and tumor types, including information from the Phase 1 study. HNSCC has been selected for investigation in Part 3. Approximately 20 to 30 patients will be enrolled in Part 3.

All included patients will satisfy the inclusion and exclusion criteria of Part 1, Part 2 or Part 3.

species) Good Laboratory Practices (GLP) toxicology study. The planned dose range (is within the maximum allowable human equivalent dose based on all available nonclinical PK and toxicology data. Dose escalation steps of are chosen to minimize the number of cohorts likely needed to meet the objectives. If needed, a smaller step change or an intermediate dose level may be selected as the next dose. Dose levels will be evaluated only as needed.

The dose escalation phase (Part 1) is anticipated to be completed with up to

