6.0 STUDY DESIGN

6.1 Description of the Study

This is a non-randomized, open-label, multi-center, safety, PK, and imaging feasibility study of ONM-100, an intraoperative fluorescence imaging agent. The study consists of 3 parts (Part 1, Part 2 and Part 3).

Part 1 will be performed in a dose-escalation design (maximum of 5 cohorts of 3 patients each) to determine the dose(s) at which ONM-100 fluorescence can be used to image metastatic lymph nodes and primary tumors

Part 2 will be a verification of the dose(s) and imaging schedule(s) from Part 1. Approximately 10 to 20 patients will be enrolled in Part 2. Eligible patients will have a confirmed diagnosis (or high clinical suspicion in the opinion of the Investigator) from among the following list of solid tumor

types

The Sponsor will inform Investigators which tumor types are open to enrollment during the conduct of Part 2.

Part 3 will investigate the safety, s Approximately 20 to 30 patients will be enrolled. Eligible patients will have a confirmed diagnosis

All included patients will satisfy the inclusion and exclusion criteria of Part 1, Part 2 or Part 3.

The starting dose level of ONM-100 his study is based on the safety, plasma exposure, and fluorescence imaging results from the Phase 1a portion of the completed Phase 1 study (ON-1001). Standard dose-escalation safety rules will be used for ONM-100 doses >1 mg/kg; note that the highest dose studied and determined to be safe in the Phase 1 Study ON-1001 was 1.2 mg/kg. Safety at each dose level will be assessed for 28 days (±48 hours) postdose in Part 1 and 28 days (±5 days) postdose in Part 2 and Part 3, and reviewed.

If needed, a smaller step change or an intermediate dose level may be selected as the next dose. Dose levels >3 mg/kg will be evaluated only as needed.

The dose escalation phase (Part 1) is anticipated to be completed with up to 5 cohorts (up to 15 patients) of the 6 potential cohorts (Table 9). Part 1 will begin with Cohort A, in which 3 patients will be administered a single dose of ONM-100 at 1 mg/kg and will undergo surgery and fluorescence imaging at \times

Protocol Amendment 6.0

Confidential

Page 66 of 125

this study, or in Study ON-1001, may be enrolled for the purposes of evaluating an alternate imaging schedule postdose, in parallel to another cohort being evaluated. All dosing decisions will be made after discussing all available data between the Sponsor and PIs and documenting the decision.

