6.2 Number of Patients

Up to 60 patients will be enrolled in this study (with planned allocation of up to 15 patients in up to 5 cohorts in Part 1, approximately 10 to 20 patients in Part 2, and approximately 20 to 30 patients in Part

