7.5 Replacement of Patients

Patients withdrawn from the study will be replaced.

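### Does the ceiling of 60 patients contradict Part allocations whose upper ends add to 65?

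*Protocol*

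**What the plan says.** The Number of Patients entry in the Protocol synopsis gives the overall limit and its breakdown in one sentence. It opens with "Up to 60 patients will be enrolled in this study (with planned allocation of up to 15 patients in up to 5 cohorts", the cohorts being those of Part 1. For the other two parts the sentence gives "approximately 10 to 20 patients in Part 2, and approximately 20 to 30 patients in Part 3". Section 6.2 repeats the limit ("Up to 60 patients will be enrolled in this study"), although its visible text breaks off before the end of the sentence. The component figures agree wherever they appear. Section 6.1 says "Part 1 will be performed in a dose-escalation design (maximum of 5 cohorts of 3 patients each", and the synopsis study design gives "Approximately 10 to 20 patients will be enrolled in Part 2" and "Approximately 20 to 30 patients will be enrolled in Part 3".

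Two provisions can add patients. The synopsis says "Up to 3 additional patients may be enrolled in the event of a DLT", and section 7.5 says "Patients withdrawn from the study will be replaced". Neither is tied to the overall limit in the visible text. The synopsis also says that the numbers in Parts 1 and 2 may differ from plan according to which cohorts, Groups and tumor types are opened. It does not mention Part 3 there. It states that no formal sample size calculation was made.

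**The concern.** Read as a budget, the sentence does not balance: the parts add to more than the total, before any patient is added after a DLT or to replace a withdrawal. Part 3 takes its dose and tumor type from the earlier results, so it enrols after them and would absorb any shortfall. It also carries the study's sensitivity and positive predictive value endpoints. If 60 binds, the part with the main diagnostic answer could not reach 30. If 60 does not bind, the sponsor would enrol more patients than the protocol states. On that view a site could not tell whether a 61st patient is permitted.

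**Working it through.** **Inputs.** Ceiling 60 (synopsis; section 6.2). Part 1: at most 5 cohorts of 3 (section 6.1). Part 2: about 10 to 20. Part 3: about 20 to 30. DLT provision: up to 3 more patients (synopsis).

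**Can 60 be reproduced?** Not as a sum of upper ends:

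- Upper ends: 5 × 3 + 20 + 30 = 65, which is 5 above 60 (5/60 = 8.3%).
- Lower ends of Parts 2 and 3 with Part 1 full: 15 + 10 + 20 = 45.
- Midpoints of Parts 2 and 3 with Part 1 full: 15 + 15 + 25 = 55.
- One midpoint and one upper end: 15 + 15 + 30 = 60, or 15 + 20 + 25 = 60.

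The protocol states no derivation. With Part 1 full, 60 lies inside the 45 to 65 that the ranges span.

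**Places left for Part 3 under the ceiling.** With k Part 1 cohorts and Part 2 at its upper end of 20, the places left are 60 - 3k - 20 = 40 - 3k:

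| Part 1 cohorts opened | Part 1 patients | Places left for Part 3 |
|---|---|---|
| 2 | 6 | 34 |
| 3 | 9 | 31 |
| 4 | 12 | 28 |
| 5 | 15 | 25 |

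The full 30 is available whenever Parts 1 and 2 together use 30 or fewer. Even with five cohorts, that needs only Part 2 at 15 or fewer.

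**Added patients, if they count toward the 60.** With Parts 1 and 2 both full, Part 3 has 25 places against a lower end of 20, so 25 - 20 = 5 further patients fit. One DLT expansion leaves 25 - 3 = 22. Two would leave 25 - 6 = 19, just below an approximate 20. In the extreme case of 3 extra patients in each of 5 cohorts, an assumption the protocol does not state, Part 1 would have 30 and Part 3 would have 60 - 30 - 20 = 10. Holding Part 2 at 10 would restore it to 60 - 30 - 10 = 20.

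**Precision.** For a patient-level proportion near 50%, exact (Clopper-Pearson) 95% half-widths are 18.7 points at n = 30, 20.4 at n = 25 and 21.8 at n = 22. Going from 30 to 25 costs 20.4 - 18.7 = 1.7 points. These figures do not measure the Part 3 primary endpoints, which the synopsis defines by counting biopsies.

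**The case for a change.** The strongest case for a change is that a protocol should not state a total that its own allocation can exceed. The arithmetic supports this: 65 is not 60. The clause on varying numbers names only Parts 1 and 2, so nothing says that Part 3 is the part to give way. The DLT provision is a live one, because section 10.5.6 sets the threshold low, at Grade 2 or above and at least possibly related to the drug. Correcting the sentence would cost little.

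The sum stands, and so does the silence about what counts toward 60. The consequence does not follow. A ceiling need not equal the sum of the upper ends when the parts are not all expected to fill. The protocol says as much for Part 1: Cohorts C to F are opened only if needed, and escalation may stop after the first two. It leaves the size of Part 2 to the sponsor's choice of tumor types and Groups. Thirty is the top of an approximate range, not a target, so comparing 25 with 30 does not show a shortfall against plan. The synopsis reports no DLT in the Phase 1 study, and section 11.8 expects little missing data. Heavy use of the extra-patient provisions is therefore not the planned case. Part of section 6.2 and the text of section 11.7 are not visible, so an accounting rule may already be there.

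**Conclusion.** The concern does not call for a change. The discrepancy is five patients between a ceiling and a sum of upper ends. Its one effect is that Part 3 cannot reach the top of its range if Parts 1 and 2 both fill. Part 3 then has 25 places, or 22 with one counted DLT expansion, and both satisfy the stated 20 to 30. A 61st patient is outside the ceiling on the plain reading that the ceiling governs the ranges.

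No estimate, test or decision rule depends on the difference. The study is descriptive, with no formal hypothesis test and no power or precision target. Whether added and replacement patients count toward the 60 is a bookkeeping question that the sponsor can settle in the enrolment records without affecting the analysis.

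This rests on two assumptions: that the ceiling takes precedence over the ranges, and that no more than five added patients are counted against it with Parts 1 and 2 both full. If more were counted, Part 3 could fall below 20 unless Part 2 were kept smaller, which the protocol already lets the sponsor do.
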